3.1.2.1 BMS-986183 Dose Expansion (Part 2)

The purpose of the BMS-986183 dose expansion (Part 2) will be to assess expanded safety experience, PK, preliminary anti-tumor efficacy, and pharmacodynamic effects of BMS-986183 monotherapy. Enrollment in cohort expansion will be determined by the GPC-3 expression of the subject's tumor sample (archival or fresh tumor sample). (See Section 3.3.1 for details regarding

tumor sample requirements; refer to the Laboratory Manual for procedures for collecting fresh tumors; and see Section 8.1.2 for adaptive design of subject enrollment during BMS-986183 dose expansion [Part 2].) Dose expansion will include subjects who are progressors or refractory on first-line treatment (see Section 3.3.1 for criteria).

Safety monitoring of subjects enrolled in BMS-986183 dose expansion (Part 2) of the study will be the same as conducted during BMS-986183 dose escalation (Part 1). During BMS-986183 dose expansion (Part 2), if the incidence of study drug-related AEs that require dose modification exceeds 29% (of treated subjects), then further enrollment to BMS-986183 dose expansion (Part 2) will be interrupted and the findings will be discussed between the Sponsor/medical monitor and investigators. An agreement will be reached as to whether a lower dose or an alternate dose schedule of BMS-986183 monotherapy should be examined, or whether any additional treatment guidelines should be implemented prior to enrollment of additional subjects on study.

Combination Therapy Extension Option

In BMS-986183 dose expansion (Part 2) only, subjects who have disease progression on BMS-986183 monotherapy will be able to receive combination treatment (their current BMS-986183 dose + flat dose of nivolumab, provided that this combination dose has been found to be safe from BMS-986183 and nivolumab dose escalation [Part 3]). This combination therapy option is not applicable during BMS-986183 dose escalation (Part 1). Eligible subjects may receive the combination option after careful evaluation and discussion with the BMS Medical Monitor to determine whether the benefit/risk ratio supports administration of further study therapy. Subjects meeting criteria for retreatment will be treated up to approximately 1 year (17 cycles, with 21 days/cycle) with a dose regimen of the combination of BMS-986183 and nivolumab dose escalation (Part 3). Such subjects must meet the eligibility criteria for receiving the combination of BMS and nivolumab as specified in Table 5.1-3.

If subjects in BMS-986183 dose expansion (Part 2) agree to receive the combination therapy, they must consent to a mandatory biopsy at clinically documented disease progression (see Section 3.3.1). In addition, subjects must wait at least 21 days since their last dose of BMS-986183 before receiving the combination therapy option, but they must receive their first dose of combination therapy within 6 weeks of their last study drug administration. These subjects will follow the assessment schedules in Table 5.1-3 and Table 5.5.1-3.

Subjects who agree to receive the combination therapy will be included in the main analysis up to and including disease progression. After disease progression, subjects who agree to receive the combination therapy will also be analyzed in a subanalysis.

3.1.2.2 BMS-986183 and Nivolumab Dose Expansion (Part 4)

The purpose of the BMS-986183 and nivolumab dose expansion (Part 4) will be to assess expanded safety experience, PK, preliminary anti-tumor efficacy, and pharmacodynamic effects of BMS-986183 and nivolumab combination therapy. Enrollment in cohort expansion will be determined by the GPC-3 expression of the subject's tumor sample (archival or fresh tumor sample). (See Section 3.3.1 for details regarding tumor sample requirements; refer to the

Laboratory Manual for procedures for collecting fresh tumors; and see Section 8.1.2 for adaptive design of subject enrollment during BMS-986183 and nivolumab dose expansion [Part 4].) Dose expansion will include subjects who have received no prior systemic therapy for HCC (see Section 3.3.1 for criteria). The dose levels of BMS-986183 and nivolumab selected for BMS-986183 and nivolumab dose expansion (Part 4) will not exceed the MTD or maximum administered dose (MAAD) of BMS-986183 and nivolumab dose escalation (Part 3) or at an alternate dose below the MTD as agreed upon by the BMS Medical Monitor and investigators.

Safety monitoring of subjects enrolled in BMS-986183 and nivolumab dose expansion (Part 4) of the study will be the same as conducted during BMS-986183 and nivolumab dose escalation (Part 3). During BMS-986183 and nivolumab dose expansion (Part 4), if the combined incidence of study drug-related AEs that require dose modification exceeds 31% (of treated subjects), then further enrollment to BMS-986183 dose expansion (Part 2) will be interrupted and the findings will be discussed between the Sponsor/Medical Monitor and investigators. An agreement will be reached as to whether a lower dose or an alternate dose schedule of BMS-986183 in combination with nivolumab should be examined or whether any additional treatment guidelines should be implemented prior to enrollment of additional subjects on study.

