Dose escalations based on incidence of DLTs/AEs:

In the absence of ADC exposure data or if the exposure does not fall below the limits described above, initial dose escalations will be in increments of up to 2-fold until the first occurrence of any of the following:

- DLT
- \geq Grade 3 decrease in neutrophil count lasting > 72 hours
- \geq Grade 3 thrombocytopenia lasting > 72 hours

Two subjects with similar \geq Grade 2 AEs that are considered related to BMS-986183 in a single dose level cohort, with the following exceptions: asymptomatic electrolyte abnormalities that can be managed with appropriate supplements and Grade 2 alopecia, fatigue, or nausea (Grade 2 fatigue or nausea that is less than 2 grades from baseline [ie, from Grade 1 to Grade 2] will not trigger a Fibonacci sequence). If 1 or more of the above occur, a modified Fibonacci dose escalation based upon DLTs will be employed for any subsequent dose escalations, and the next immediate escalation increment will be a maximum of 67% of the current dose followed by

increments of 50%, 40%, and 33% respectively for each subsequent dose escalation. If the mTPI algorithm indicates that escalation should continue beyond the first 33% increase, any further dose escalations will be in increments of 33% of the current dose.

In the absence of DLTS or AEs, in the initial four dose levels during dose escalation, then dose escalation will proceed as above. A modified Fibonacci based escalation will be triggered after dose level 4 and no further 2 fold increase in dose will be employed thereafter.

BMS-986183 Dose Escalation (Part 1): Dose Escalation Decision Rules

Enrollment in dose escalation and selection of the MTD will adhere to an mTPI design. The mTPI design provides a simple algorithm for decisions on escalation, expanding at the same dose, and de-escalation, depending on the number of observed toxicities after each dose level cohort (see Figure 3.1.1.1-1). The mTPI method utilizes a target toxicity (DLT) rate and equivalence interval (EI) to make decisions on escalation after each cohort and to estimate the MTD. For this study the target DLT rate is 27% and the EI is 25% to 29%.

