As in BMS-986183 dose escalation (Part 1), an mTPI design (Table 3.1.1.2-1) will be used to guide dose-escalation decisions and to select the MTD. A DLT target rate of 29% (EI = [27%, 31%]) will be used for combination therapy to guide escalation decisions. Dose-escalation decisions will be based on the total number of subjects in a dose level who are DLT evaluable and the number of DLTs observed at that dose level, guided by the mTPI Bayesian model and posterior inference.

The number of subjects in the initial cohort of each dose level will be 3 to 4. The fourth subject may be enrolled following agreement between the investigator and the Sponsor/Medical Monitor if able to start the first day of dosing within approximately 1 week of the third subject in the same dose-escalation cohort. The DLT evaluation period will be 21 days. See Section 4.5.1 for further details of DLT evaluation. Enrollment of additional cohorts at the same dose level will proceed in sample sizes of up to 3 or 4 subjects. Subsequent dose levels will follow similar cohort enrollment size and decision rules. At least 3 DLT evaluable subjects at each of the dose levels in BMS-986183 and nivolumab dose escalation (Part 3) will be required to enable a decision to escalate, add more subjects to the current dose level, or de-escalate and declare the current dose as unacceptable (ie, exceeding the MTD). Subjects with insufficient data to establish safety during the DLT evaluation period at a dose level may be replaced upon agreement of the BMS Medical Monitor and investigators.

Dose Selection for BMS-986183 and Nivolumab Dose Expansion (Part 4)

At the end of the BMS-986183 and nivolumab dose-escalation period, the cumulative number of subjects who experience a DLT at each dose level will be used to estimate the MTD of BMS-986183 in combination with nivolumab using isotonic regression. The MTD will be selected as the dose level with the smaller difference of estimated toxicity rate and the target DLT rate among the dose levels explored.

Once the safety (during DLT evaluation) of a dose level has been determined, additional subjects may be added at that dose to better characterize the PK, safety, and pharmacodynamic profile or to satisfy regional/local requirements (eg, in Chinese subjects where weight or genetic factors may play a role in safety, PK, and pharmacodynamics).

3.1.2 Dose Expansion (BMS-986183 Dose Expansion [Part 2] and BMS-986183 and Nivolumab Dose Expansion [Part 4])

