7 DATA MONITORING COMMITTEE AND OTHER EXTERNAL COMMITTEES

Not applicable.

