Under 1) if 0 responses are observed with mH-score \geq 150 (and no other responses in the study population for the expansion cohort are observed), then the expansion cohort may stop for futility. More generally, the statistical method to guide the determination of insufficient response is Bayesian predictive probability.⁸² Under 1), if predictive probability of success is less than a pre-specified futility threshold, where success means a posterior response rate is greater than the target null efficacy rate with a very high probability at the end of study, the expansion cohort may stop for futility. A decision to stop the expansion cohort will be based not only on response but also on the totality of the safety, efficacy, and PK/pharmacodynamic data.

Under 2) if 0 responses are observed with mH-score < 50 and cytoplasmic H-score \geq 50, then the study population may be restricted to mH-score \geq 50. More generally, if predictive probability of success is less than a pre-specified futility threshold, where success means a posterior response rate is greater than the target null efficacy rate with a very high probability at the end of study, the expansion cohort may be restricted to mH-score \geq 50.

Enrollment will continue while interim analyses are conducted. For the remainder of the dose expansion, assuming the study is not stopped for futility, ongoing assessment of the responses may result in 3 additional adaptations, depending on whether 1) or 2) is achieved first. If 1) occurs first, then when 2) occurs, if predictive probability is less than a pre-specified futility threshold, the study population may be restricted to mH-score ≥ 50 . If 2) occurs first, then when 1) occurs, if predictive probability is less than the pre-specified futility threshold, the study may be stopped for futility.

The third possible adaptation may be considered once the population is restricted to mH-score ≥ 50 . Depending on the number of responses in the mH-score < 150 (ie, if 0 responses) enrollment may be further restricted to subjects with mH-score ≥ 150 . Once the biomarker threshold is identified, the cohort may be expanded to ensure adequate subjects from the finalized population of interest for achieving a reasonable precision of ORR.

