8.5 Interim Analyses

Because the exploratory nature of the early phase study, data emerging from each dose level or each part of the study will be examined prior to the formal locking of the study database for timely decisions about, such as but not limited to, dose selection, regimen selection and early termination of the study. There will be no formal hypothesis testing, nor will multiplicity be adjusted.

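### The Part 4 toxicity rule interrupts enrolment to Part 2, so crossing the 31% combination limit does not, as written, pause Part 4.

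*Protocol*

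**What the plan says.** Section 3.1.2.2 of the Protocol governs Part 4, the expansion of BMS-986183 with nivolumab in subjects with no prior systemic therapy. Its safety rule is triggered by the combined incidence, during Part 4, of study drug-related adverse events that require dose modification. If that incidence "exceeds 31% (of treated subjects), then further enrollment to BMS-986183 dose expansion (Part 2) will be interrupted". The sponsor or medical monitor and the investigators then discuss the findings. They agree whether a reduced dose or a changed regimen "in combination with nivolumab should be examined or whether any additional treatment guidelines should be implemented prior to enrollment of additional subjects on study".

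The parallel rule for the monotherapy expansion is in Section 3.1.2.1. There, if the incidence "exceeds 29% (of treated subjects), then further enrollment to BMS-986183 dose expansion (Part 2) will be interrupted", the same kind of discussion follows about the monotherapy dose.

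The synopsis does not repeat the Part 4 rule. The SAP neither restates nor corrects it: SAP Section 7.5.5 only tabulates and lists adverse events that led to dose delay, interruption or reduction.

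**The concern.** The trigger and the action concern different cohorts. Toxicity is counted in subjects on the combination, but the only enrolment interrupted is that of subjects on monotherapy, who do not receive the regimen that crossed the limit. If Part 2 had already finished accruing, the ordered interruption would stop nobody.

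The clause matters because nothing else does its job. If it is followed literally, Part 4 has no pre-specified toxicity threshold that pauses enrolment, in a study where one of the two agents is being given to humans for the first time.

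**Working it through.** The point is one of wording, and the plan gives no figure to reproduce. The check has three steps.

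**1. The two expansion rules side by side**

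| Element | Part 2 rule (3.1.2.1) | Part 4 rule (3.1.2.2) |
|---|---|---|
| Event counted | Drug-related AEs requiring dose modification | The same, as a combined incidence |
| Cohort counted | Part 2 | Part 4 |
| Limit | Above 29% of treated subjects | Above 31% of treated subjects |
| Enrolment interrupted | Part 2 | **Part 2** |
| Remedy discussed | Monotherapy dose or schedule | Combination dose or schedule |

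Every element was adapted for Part 4 except the cohort to be interrupted. The limits fit that reading. In Section 3.1.1.1 the monotherapy target DLT rate is 27% with an equivalence interval of 25% to 29%. In Section 3.1.1.2 the combination target is 29% with an interval of 27% to 31%. Each expansion limit equals the upper end of its own regimen's interval. The revision history also shows that the combination parts were added by Amendment 02, which fits a clause carried over from the older monotherapy text.

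**2. Is there another rule that pauses Part 4?**

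- Section 3.1 limits the DLT assessment period to Parts 1 and 3.
- Sections 4.5.1 to 4.5.6 govern dosing of individual subjects, not cohort enrolment.
- Section 8.1.2 covers futility and H-score adaptation. A decision to stop a cohort there also weighs the "totality of the safety, efficacy, and PK/pharmacodynamic data", but no toxicity limit is given.
- Section 8.5 says that "data emerging from each dose level or each part of the study will be examined prior to the formal locking of the study database". That is discretionary review without a threshold.
- Section 7, on a data monitoring committee, reads "Not applicable".
- The SAP contains no stopping or pausing rule for toxicity.

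None of these orders a pause of Part 4 enrolment at a stated toxicity rate.

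**3. Scale**

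Inputs: the 31% limit (Section 3.1.2.2) and about 50 planned Part 4 subjects (Section 8.1.2). The values of n are illustrative and span the cohort. The smallest count over the limit is k = floor(0.31 × n) + 1, and the planned subjects remaining are 50 − n.

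| Treated, n | 0.31 × n | Smallest k over 31% | k/n | Planned subjects remaining |
|---|---|---|---|---|
| 10 | 3.1 | 4 | 40.0% | 40 |
| 20 | 6.2 | 7 | 35.0% | 30 |
| 30 | 9.3 | 10 | 33.3% | 20 |
| 40 | 12.4 | 13 | 32.5% | 10 |
| 50 | 15.5 | 16 | 32.0% | 0 |

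No probability of crossing is given, because the documents state neither an expected rate of dose-modifying events nor a schedule for checking the rule.

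**The case against.** The strongest reply is that no sensible reader would be misled. The rule stands under the Part 4 heading, its trigger names Part 4, its remedy concerns the combination, and its closing words about enrolling further subjects presuppose a hold. Part labels slip elsewhere in the Protocol too: footnotes to the assessment schedule call Part 2 dose escalation. This is right about intent. It does not supply the missing order, since the closing words say when agreed changes take effect and the only interruption ordered is of Part 2. Section 9.1.1 also requires the study to be conducted as the approved protocol describes.

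A second reply is that treated Part 4 subjects are still protected. Dosing is held, modified or stopped under Sections 4.5.1 to 4.5.6, the dose may not exceed the Part 3 MTD or maximum administered dose, and the sponsor can stop at its discretion. This also stands, and it lowers the practical risk. But those provisions manage subjects already on treatment or leave the decision open. They do not replace a rule on enrolling new subjects.

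A third is that the link between the limits and the equivalence intervals is inferred. The intervals concern DLT rates over 21 days, the expansion rules count a different event with no such window, and no section connects them. That is fair, but the mismatch is visible in the sentence without it.

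A fourth is that naming Part 2 might be deliberate, because Part 2 subjects may receive the combination after progression (Section 3.1.2.1). Those subjects are already enrolled, so interrupting new Part 2 enrolment would not stop their combination dosing.

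Last, the tabulated counts are not necessarily first crossings. The rule has no minimum n, so 1 of 3 (33.3%) already exceeds 31%. The table shows scale only.

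**Conclusion.** The concern holds. As written, crossing the 31% combination limit interrupts the monotherapy cohort and starts a discussion of the combination, but does not order a pause of Part 4. Depending on when the limit is crossed, up to about 40 of the 50 planned Part 4 subjects (crossing seen at 10 treated) and as few as none (crossing seen at 50) remain to be enrolled without an ordered hold. These figures assume the planned size of about 50 and checks at the illustrative values of n.

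The finding rests on the literal text. The intended meaning is very probably a Part 4 pause, and a sponsor acting on that intent would pause it. It should still be corrected, because this is the only pre-specified toxicity pause that Part 4 has and sites should not have to infer which cohort stops.

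**What to change.** In the interruption clause of Section 3.1.2.2, replace the reference to BMS-986183 dose expansion (Part 2) with BMS-986183 and nivolumab dose expansion (Part 4). Keep the 31% limit and the rest of the paragraph.

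If the sponsor also wants new Part 2 enrolment, or the combination extension option for Part 2 subjects, held when the combination limit is crossed, it should say so in a separate sentence.

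The cost is a one-phrase protocol correction. It needs no new data and changes no sample size or analysis.

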3.2 Post Study Access to Therapy

At the end of the study, BMS will not continue to provide BMS supplied study drug to subjects/investigators unless BMS chooses to extend the study. The investigator should ensure that the subject receives appropriate standard of care to treat the condition under study.

3.3 Study Population

For entry into the study, the following criteria MUST be met prior to dosing on Day 1. No exceptions will be granted.

3.3.1 Inclusion Criteria

1) Signed Written Informed Consent

a) The subject must sign the ICF prior to the performance of any study-related procedures that are not considered part of standard of care.

2) Target Population

- a) Subjects with advanced HCC not amenable for management with curative intent by surgery or local therapeutic measures.
- b) Histological confirmation of HCC. Subjects with radiological diagnosis may be enrolled for screening in the study but histological confirmation is mandatory prior to initiation of study therapy.
- c) Subjects must fulfill the criteria for prior therapy and GPC-3 expression as follows:
 - i) For BMS-986183 dose escalation (Part 1) and BMS-986183 and nivolumab dose escalation (Part 3): Subjects with HCC must have received and either progressed or been refractory or intolerant to at least 1 standard prior systemic treatment regimen. Subjects who refuse or are ineligible for standard therapy will be allowed to enroll provided their refusal/ineligibility is documented in medical records.

- ii) For BMS-986183 dose expansion (Part 2): Only subjects with HCC who have progressed or been refractory to at least 1 standard prior systemic treatment regimen (and not received more than 2 prior systemic treatments) AND with a plasma membrane or cytoplasmic H score ≥ 50 for GPC-3 expression (as defined in Section 5.6.1) in the tumor tissue.
- iii) **BMS-986183 and nivolumab dose expansion (Part 4)**: No prior systemic therapy for HCC AND with a plasma membrane or cytoplasmic H score \geq 50 for GPC-3 expression (as defined in Section 5.6.1) in the tumor tissue.
- d) For BMS-986183 dose escalation (Part 1) and BMS-986183 and nivolumab dose escalation (Part 3): A tumor tissue block or unstained slides of tumor sample (archival or recent and not older than 3 months from time of slide preparation) must be provided for biomarker evaluation, as described in Section 5.6.
 - i) Subjects must consent to allow the acquisition of tumor block or a minimum of 10 slides for performance of correlative studies; attempts should be made to collect a maximum of 20 unstained slides. Individual sample availability should be discussed with the Sponsor if at least 10 slides are not available for any subject.
 - ii) Subjects have the option to also provide fresh pre- and post-treatment biopsies. The post-treatment biopsy should be obtained on Cycle 2, 24 to 48 hours post dose and at any other time an investigator chooses to obtain a biopsy during the study period. These biopsies are not mandatory but are highly encouraged. If a subject opts to have the post-treatment biopsy taken, then a fresh tumor biopsy at screening will be mandatory because it will serve as a baseline sample with which data from the post-treatment biopsy will be compared. For both biopsies, subjects must have a soft tissue tumor lesion that can be biopsied at acceptable clinical risk (as judged by the investigator).
 - iii) If archival slides do not meet the requirements (minimum 10 slides and not older than 3 months from time of slide preparation) or are not available, then slides from a fresh biopsy will be used to assess GPC-3 expression.
- e) For BMS-986183 dose expansion (Part 2) and BMS-986183 and nivolumab dose expansion (Part 4): A tumor tissue block or unstained slides of tumor sample (archival or recent and not older than 3 months from time of slide preparation) is mandatory for biomarker evaluation, as described in Section 5.6.
 - i) Subjects must consent to allow the acquisition of existing tumor block or a minimum of 10 slides for performance of correlative studies; attempts should be made to collect a maximum of 20 slides. Individual sample availability should be discussed with the Sponsor if at least 10 slides are not available for any subject.
 - ii) In addition to archived samples, a fresh biopsy sample is mandatory at screening. For this biopsy, subjects must have a soft tissue tumor lesion that can be biopsied at acceptable clinical risk (as judged by the investigator) at baseline. Subjects must consent to the pretreatment fresh biopsy as a condition of protocol participation. In this setting, if adequate tissue is not obtained during the first procedure then a repeat biopsy should be considered based on the investigator's assessment of clinical risk. However, a repeat biopsy is not required to meet eligibility in BMS-986183 dose escalation (Part 1).

- iii) Both archived biopsy/slides and slides from fresh biopsy will be used for determining eligibility in BMS-986183 dose expansion dose expansion (Part 2) or BMS-986183 and nivolumab dose expansion (Part 4) based on GPC-3 expression (see Section 5.6 for details regarding GPC-3 expression cut-off required for eligibility). If the fresh biopsy meets defined cut-off criteria for GPC-3 expression, then the subject will be eligible. If the fresh biopsy does not meet defined cut-off criteria for GPC-3 expression, then the subject will not be eligible. If the archival slides meet defined cut-off criteria for GPC-3 expression and data from the fresh sample are not evaluable, then the subject will be eligible. If the archival slides do not meet the requirements (a minimum of 10 slides and not older than 3 months from time of slide preparation) and data from the fresh sample are not evaluable, the fresh sample and only fresh tumor biopsy can be obtained for assessing eligibility, such subjects can be enrolled in study after discussion with the Sponsor.
- iv) A mandatory fresh post-treatment biopsy is to be obtained at Cycle 2, 24 to 48 hours post dose from 20 subjects enrolled in BMS-986183 dose expansion (Part 2) and from 20 subjects enrolled in BMS-986183 and nivolumab dose expansion (Part 4). The biopsy is optional but highly encouraged for the other 30 subjects enrolled in BMS-986183 dose expansion (Part 2) and BMS-986183 and nivolumab dose expansion (Part 4). If 20 subjects out of the first 30 subjects enrolled in BMS-986183 dose expansion (Part 2) and BMS-986183 and nivolumab dose expansion (Part 4). Post-treatment biopsies can also be obtained at any other time an investigator chooses to obtain a biopsy during the study period. For tumor biopsies, subjects must have a soft tissue tumor lesion that can be biopsied at an acceptable clinical risk (as judged by the investigator).
- v) Lesions selected for biopsy should be large enough to allow for the collection of tumor tissue using a minimum 18-gauge or larger needle with an expected core sample length of 5 mm. A minimum of 2 passages of the needle core should be obtained. If adequate tissue is not obtained following initial passages of the needles, repeat passages of the needle should be performed if clinically feasible. Smaller lesions may be biopsied or smaller gauge needles may be used provided adequate tissue can be collected (similar quantity to amount collected using 18-gauge thickness and 5-mm core length). Refer to the Laboratory Manual for further details on procedures for collecting fresh tumors.
- vi) Biopsies at clinically documented disease progression are optional but highly encouraged. At the time of clinically documented disease progression, if a subject enrolled in BMS-986183 dose expansion (Part 2) agrees to receive combination therapy, then the biopsy at clinically documented disease progression is mandatory (see also Section 3.1.2.1).
- vii) The immediate confirmation (eg, touch imprint cytopathology) for presence of viable tumor cells from collected tissue samples is strongly recommended.
- f) Cirrhotic status of Child-Pugh Class A, that is, Child-Pugh Score of 6 points or less (Appendix 4).

- g) ECOG Performance Status of 0 to 1 (Appendix 5).
- h) Subjects are eligible to enroll if they have nonviral-HCC or if they have HBV- or HCV-HCC, defined as follows:
 - i) HBV-HCC: Resolved HBV infection (as evidenced by detectable HBV surface antibody, detectable HBV core antibody, undetectable HBV deoxyribonucleic acid [DNA], and undetectable hepatitis B surface antigen [HBsAg]) or chronic HBV infection (as evidenced by detectable HBsAg, hepatitis B e antigen [HBeAg], or HBV DNA). Subjects with chronic HBV infection must have HBV DNA < 500 IU/mL and must be on antiviral therapy per regional standard of care guidelines prior to initiation of study therapy. All subjects enrolled with HBV must continue antiviral therapy through the follow-up period of the study. Both HBeAg-positive and -negative subjects will be included. Subjects with chronic HBV who are not on antiviral therapy at screening cannot be enrolled in the study.
 - ii) HCV-HCC: Active or resolved HCV infection as evidenced by detectable HCV ribonucleic acid (RNA) or antibody, respectively. Subjects on antiviral therapy for hepatitis C are permitted and should continue treatment during the study up to the follow-up period. Subjects with active HCV who are not on antiviral therapy at screening cannot be enrolled in the study.
- i) At least 1 RECIST v1.1 previously untreated, unidimensionally measurable lesion by contrast-enhanced tri-phasic computed tomography (CT ≥ 10 mm or contrast-enhanced dynamic magnetic resonance imaging (MRI) scan ≥ 10 mm (malignant lymph nodes must be ≥ 15 mm on short axis) (additional details are included in Appendix 6)⁸¹
 - i) The lesion can be accurately measured unidimensionally according to RECIST v1.1
 - ii) The lesion has not been previously treated with surgery, radiotherapy, and/or locoregional therapy (eg: radiofrequency ablation, percutaneous ethanol or acetic acid injection, cryoablation, high-intensity focused ultrasound, transarterial chemoembolization, transarterial embolization, etc.)
 - iii) Previously treated lesions can be considered target lesions if there is clear evidence of progression.
 - iv) Bone metastases are not considered measurable lesions, unless there is a measurable soft tissue component per RECIST v1.1 (see Appendix 6).⁸¹
 - v) The measurable lesion cannot be biopsied during treatment (if there is only 1 lesion).
- j) For subjects who progressed after locoregional therapy, locoregional therapy for HCC must be completed at least 4 weeks prior to the baseline scan. All acute toxic effects of any prior local treatment must have resolved to NCI CTCAE v4.03 Grade ≤ 1 or been deemed irreversable.

Screening laboratory values must meet the following criteria:

- i) Adequate hematologic function:
 - (1) Neutrophils $\geq 1500/\mu L$

- (2) Platelets $\ge 60 \times 10^3/\mu L$ (transfusion to achieve this level is not permitted within 2 weeks of first study drug administration)
- (3) Hemoglobin \ge 8.5 g/dL (may be transfused to meet this requirement within 2 weeks of first study drug administration)
- (4) Prothrombin time (PT)-international normalized ratio (INR) ≤ 2.3 or PT ≤ 6 seconds above control.
- ii) Adequate hepatic function
 - (1) Albumin $\geq 2.8 \text{ g/dL}$
 - (2) Total bilirubin $\leq 3 \text{ mg/dL}$
 - (3) AST \leq 5 × the institutional ULN
 - (4) ALT \leq 5 × the institutional ULN

iii) Adequate renal function with a serum creatinine of $< 1.5 \times ULN$ or a creatinine clearance (CrCl) > 40 mL/min using Cockcroft-Gault formula below:

Female CrCl = $(140 - age in years) \times weight in kg \times 0.85$ $72 \times serum creatinine in mg/dL$ Male CrCl = $(140 - age in years) \times weight in kg \times 1.00$ $72 \times serum creatinine in mg/dL$

- k) Ability to comply with treatment, PK and research sample collection (when indicated), and required study follow-up.
- Subject Re-enrollment: This study permits the re-enrollment of a subject that has discontinued the study as a pretreatment failure (ie, subject has not been treated). If re-enrolled, the subject must be re-consented.

3) Age and Reproductive Status

- a) Males and Females, ages 18 or age of majority
- b) Women of childbearing potential (WOCBP) must have a negative serum or urine pregnancy test (minimum sensitivity 25 IU/L or equivalent units of human chorionic gonadotropin) within 24 hours prior to the start of study drug.
- c) Women must not be breastfeeding.
- d) WOCBP must agree to follow instructions for method(s) of contraception for the duration of treatment with study drug (s) BMS-986183 monotherapy plus 5 half-lives of study drug plus 30 days (duration of ovulatory cycle) for a total of 90 days post-treatment completion (BMS-986183 dose escalation [Part 1] and BMS-986183 dose expansion [Part 2]). WOCBP must agree to follow instructions for method(s) of contraception for the duration of study treatment with nivolumab and 5 months (150 days) after the last dose of study drug (ie, 30 days [duration of ovulatory cycle] plus the time required for the study drug to undergo approximately 5 half-lives) (BMS-986183 and nivolumab dose escalation [Part 3] and BMS-986183 and nivolumab dose expansion [Part 4]).

- e) Males who are sexually active with WOCBP must agree to follow instructions for method(s) of contraception for the duration of treatment with study drug (s) BMS-986183 plus 5 half-lives of the study drug plus 90 days (duration of sperm turnover) for a total of 150 days post-treatment completion (BMS-986183 dose escalation [Part 1] and BMS-986183 dose expansion [Part 2]). Males who are sexually active with WOCBP must agree to follow instructions for method(s) of contraception for the duration of study treatment with nivolumab and 7 months (210 days) after the last dose of study drug (ie, 90 days [duration of sperm turnover] plus the time required for the study drug to undergo approximately 5 half-lives). In all study parts, male subjects must be willing to refrain from sperm donation during the time described above.
- f) Azoospermic males are exempt from contraceptive requirements. WOCBP who are continuously not heterosexually active are also exempt from contraceptive requirements and still undergo pregnancy testing as described in this section.

Investigators shall counsel WOCBP and male subjects who are sexually active with WOCBP on the importance of pregnancy prevention and the implications of an unexpected pregnancy. Investigators shall advise on the use of highly effective methods of contraception, which have a failure rate of < 1% when used consistently and correctly. Refer to Appendix 7.

